NCT03168867

Effectiveness Trial of an E-Health Intervention To Support Diabetes Care in Minority Youth (3Ms) 3/20/23

Study Protocol with Statistical Analysis Plan

The effectiveness trial is a multi-site clinical trial using a randomized, controlled, repeated measures design to test the effects of a computer delivered eHealth parenting intervention to improve health outcomes among African American adolescents with type 1 diabetes (T1D). The study will be conducted at 3 clinics in the Detroit area and 4 clinics in the Chicago area. 212 African American (AA) adolescents with type 1 diabetes and their primary caregivers will be enrolled. Study consent and the baseline assessment session will be completed in the diabetes clinic at the time of a regularly scheduled medical appointment Families will be randomized to one of two arms: *The 3Ms* intervention (to increase parental motivation for monitoring of adolescent DSM) or *standard control*. Participants will be allocated to the treatment arm using block randomization within 8 strata defined by the four sites and HbA1c level (most recent HbA1c ≤9.5% vs. >9.5%). Within these strata, the software will randomly assign participants to conditions in a 1:1 ratio to ensure equivalence in each condition.

Parents will complete the first intervention session in the diabetes clinic immediately after baseline data collection and randomization. The subsequent two intervention sessions will also be conducted during regularly scheduled diabetes clinic visits and can be completed any time in the 12-month window after baseline assessment. American Diabetes Association standards of care for youth with diabetes specify that visits to a diabetes specialty care center should occur quarterly; therefore, participants should be seen in clinic four times in a 12-month window. *The 3Ms* intervention is designed to be delivered over nine months should families receive diabetes care at the recommended frequency. Data collection will occur on a different schedule than intervention sessions and will occur at regularly scheduled visits conducted at six months and 12 months after baseline data collection. It is also important to note that while the 12-month data collection visit will typically occur 12 months from baseline, it must also occur at least 30 days from the date of the last intervention session (so that any changes in HbA1c occurring as a result of the intervention can be detected). The data analyses to be used in the study can accommodate varying lengths of time between data collection sessions. A final data collection session will be conducted 18 months after baseline to assess stability of intervention effects in the 6 months after intervention completion.

Participants will be 212 African American adolescents aged 10 years, 0 months -13 years 11 months diagnosed with T1D for a minimum of six months, and their parents. Given that this is an effectiveness trial, exclusion criteria are kept to a minimum so that transportability to real-world settings is adequately assessed. No exclusions will be made due to co-morbid mental health problems (e.g. ADHD, conduct disorder, depression), with the exception of schizophrenia/other psychosis, current suicidality or homicidality. Adolescents with cognitive impairments are also excluded if those impairments are severe enough to result in inability to complete research measures or impact their independence with diabetes care. Finally, if potential subjects have diabetes secondary to another chronic medical illness (e.g. cystic fibrosis) and their medical management differs substantially from that of most children with type 1 diabetes, they will be excluded.

All measures will be administered at baseline, 6, 12 and 18 months. The primary outcome glycemic control will be measured via hemoglobin A1c (HbA1c). HbA1c will be obtained using the Accubase A1c test kit manufactured by Diabetes Technologies. The Accubase test is FDA approved and uses a capillary tube blood collection method instead of venipuncture. It is therefore suitable for home-based data collection. High performance liquid chromatography (HPLC) is used to analyze the blood sample. Samples are stable for up to 30 days unrefrigerated and vials are bar coded to ensure confidentiality but minimize the likelihood of data loss. Secondary outcomes are measures by questionnaire self-report and/ or parent report.

In the preliminary study, the pooled standard deviation estimate for HbA1c change was 1.34%. If a sample size for the planned analyses is approximated by a t-test for the change in HbA1c from baseline to 12 or 18 months, a sample size of 97 per study arm will allow difference of 0.6% in HbA1c (based on our pilot data and the clinical significance of a 0.5% change), to be detected with 80% power (alpha = 0.025). If 106 families are enrolled per arm, a net sample size of 97 allows for 8% subject attrition/loss to follow-up. Our retention rates in our pilot study were 94%. A sample of this size is also sufficient to identify moderator variables that account for 7% increment in outcome variance using moderated regression analysis. Since outcome data will be collected during home visits, and even patients with incomplete data will contribute to the effective net sample size, the planned sample size is considered feasible with a total of 212 participants enrolled (106 3Ms, 106 control).

The primary outcome will be analyzed using the linear mixed effect model (LME) for repeated measures. Contrasts on the repeated measures [baseline minus 6-month, baseline minus 12-month (end of treatment), and baseline minus 18-month (6-month follow-up)] will partition the main effect of time. Three single degree of freedom contrasts will be defined by crossing the treatment arm factor with each time contrast; the latter two contrasts will test the primary hypotheses at intervention completion and six-month follow-up. The analysis will

be intent-to-treat (ITT) and will include all randomized participants regardless of the intervention dose received. In addition, attrition will be minimized by retention methods used successfully in our prior studies. Potential control variables include sociodemographic and clinical variables. If the baseline values are not equal for the intervention and control groups, we will consider adding covariates before testing the intervention effect. Moderated regression analysis will be used to investigate variables that might moderate treatment effects (e.g. youth executive functioning, youth depression,or level of family conflict). Product terms involving the moderator and the time x treatment contrasts will be added to the LME model one at a time. These interaction contrasts will estimate the increment in outcome variance accounted for by the moderator.

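### The primary mixed model does not pre-specify the randomisation factors (site, HbA1c stratum) by visit; if the strata predict HbA1c change, the reported standard error is too large, by 0% to about 9% in the scenarios examined.

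*Combined protocol and SAP*

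**What the plan says.** All references are to the combined protocol and SAP, whose sections are unnumbered.

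- **Design paragraph.** Allocation is by "block randomization within 8 strata defined by the four sites and HbA1c level", with the HbA1c level defined as "most recent HbA1c ≤9.5% vs. >9.5"%. Within strata, "the software will randomly assign participants to conditions in a 1:1 ratio".
- **Sample-size paragraph.** The calculation approximates the analysis by a t-test on change, where "the pooled standard deviation estimate for HbA1c change was 1.34"%. It gives 97 per arm for a 0.6% difference with 80% power at alpha 0.025, and 106 enrolled per arm.
- **Primary-analysis paragraph.** The model is a linear mixed model for repeated measures with baseline-minus-follow-up time contrasts. "Three single degree of freedom contrasts will be defined by crossing the treatment arm factor with each time contrast"; those at 12 and 18 months test the primary hypotheses. Neither site nor HbA1c stratum is named as a model term.
- **Covariates, same section.** "Potential control variables include sociodemographic and clinical variables". Then: "If the baseline values are not equal for the intervention and control groups, we will consider adding covariates before testing the intervention effect".

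**The concern.** Blocking within strata removes between-stratum variation from the arm comparison. A model without the strata leaves that variation in the residual, so it reports a standard error larger than the true one. Because the contrasts are differences from baseline, this matters only as far as the strata predict *change* in HbA1c, not its level.

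The covariate rule is unlikely to close the gap. It responds to baseline differences between arms, and 1:1 blocks within strata make differences on these two factors unlikely. It also sets no threshold for unequal and only promises to consider adjustment, so the form of the primary model may be settled after data are seen.

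At stake is precision. The confidence intervals for the two primary contrasts may be wider than the design warrants, and a gain that is almost free may be missed.

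**Working it through.** **Inputs from the plan:** 97 per arm net, SD of change 1.34, difference 0.6, alpha 0.025, 106 enrolled per arm. Sidedness is not stated; two-sided reproduces the stated figure.

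**Not in the plan, assumed:** R², the share of the variance of HbA1c change explained by the strata. The simulations also assume blocks of 4, four equal sites, a median split at 9.5%, the HbA1c correlations, and a site SD on change of 0 or 0.3.

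**1. The plan's own figure.** SE = 1.34 × √(2/97) = 0.1924. Noncentrality is 0.6/0.1924 = 3.118 on 192 degrees of freedom. The two-sided t-test at 0.025 has 80.4% power, and 97 is the smallest sample per arm that reaches 80%. Since 106 × 0.92 = 97.5, the enrolment figure also reproduces. A one-sided 0.025 test would need only about 80 per arm.

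**2. Effect of omitting the strata.** Under stratified blocks the true SE is 0.1924 × √(1 − R²), while the model without strata still reports 0.1924. The excess is 1/√(1 − R²) − 1.

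| R² | True SE | SE excess | Type I error, unadjusted | Power, unadjusted | Power, adjusted |
|---|---|---|---|---|---|
| 0 | 0.1924 | 0% | 0.025 | 80% | 80% |
| 0.05 | 0.1875 | 2.6% | 0.022 | 81% | 83% |
| 0.10 | 0.1825 | 5.4% | 0.018 | 82% | 85% |
| 0.15 | 0.1774 | 8.5% | 0.015 | 82% | 87% |

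A 9% excess corresponds to R² = 0.158.

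**3. What R² might be.** For a median-split stratum with equal SDs, write r(c,b), r(c,f) and r(b,f) for the correlations clinic–baseline, clinic–follow-up and baseline–follow-up. Then R² = (2/π) × (r(c,f) − r(c,b))² / [2(1 − r(b,f))]. It is zero when the clinic value correlates equally with baseline and follow-up. Change scores were simulated with 194 completers, 20,000 replicates per setting and total SD of change held at 1.34:

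| r(c,b) / r(c,f) / r(b,f) | SE excess, no site effect | SE excess, site SD 0.3 |
|---|---|---|
| 0.7 / 0.7 / 0.7 | about 0% | 1.9% |
| 0.8 / 0.65 / 0.7 | 1.0% | 3.4% |
| 0.9 / 0.63 / 0.7 | 3.4% | 6.8% |
| 0.9 / 0.45 / 0.5 | 7.8% | 9.3% |

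Across these settings power was 80–82% unadjusted and 80–88% adjusted. Where the strata predicted nothing, adjusting cost about 0.1 point (80.1% to 80.0%).

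**4. Four-visit mixed model.** This used an unstructured covariance, 106 per arm, dropout reaching 8% at 18 months and 3,000 replicates per setting. The SE excess ran from about 0% to roughly 6–10%, with Monte Carlo error of about 1.3% on the ratio. Power for the 18-month contrast, without and with strata by visit:

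- Strata predict nothing: 82.8% and 83.0%.
- 0.9 / 0.63 / 0.7: 83.5% and 85.4%.
- 0.9 / 0.45 / 0.5 with site SD 0.3: 84.7% and 89.1%.

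**5. Why by visit.** Stratum main effects shift every visit equally and cancel from a baseline-minus-follow-up contrast. With complete data the estimate and SE were identical to the unadjusted model (SE ratio 1.0000); with 8% dropout the ratio was 0.999–1.002. A separate four-visit check, with the stratum cut on the baseline value and within-person correlation 0.5, gave reported/true SE ratios of 1.11 without strata, 1.11 with main effects only and 1.02 with strata by visit.

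**The case against.** The strongest reply is that no harm is shown. The estimate is unbiased, type I error is not inflated, and the planned power holds without adjustment. All of that is correct and limits the weight of the point.

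Second, the size is assumed. The larger figures need a clinic value that tracks baseline closely and follow-up poorly. The stratum uses the most recent HbA1c, which may be a separate earlier measurement: the outcome comes from a capillary sample analysed by HPLC, and the first session immediately follows baseline collection and randomisation. With exchangeable correlations the SE ratio is then about 1.00. This stands, and it is why the lower end is 0%. Nor is 9% a ceiling: R² of 0.20 or 0.25 would give 11.8% or 15.5%.

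Third, conditioning on baseline HbA1c can do better. At 0.9/0.45/0.5 without a site effect, it gave an SE of 0.167 with or without strata, against 0.179 for strata by visit alone. At 0.9/0.63/0.7 the figures were 0.177 and 0.185. The plan does not say whether baseline means are constrained to be equal; if they are, less is gained from the strata. That also stands, but it does not make strata redundant. Baseline-adjusted models without strata still had reported/true SE ratios of 1.04 and 1.08 in some settings.

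Fourth, clinical control variables could include HbA1c level, and an HbA1c difference within strata could trigger adjustment. That is possible but discretionary, and site is not named.

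**Conclusion.** The concern holds. The plan randomises on site and HbA1c level but does not commit the primary model to either factor, and its covariate rule is unlikely to supply them. If the strata predict HbA1c change, the reported standard errors of the 12- and 18-month contrasts are too large: 0% to 8.5% for R² of 0 to 0.15, and up to about 9% in the simulated change scores. The corresponding power forgone is 0 to 5 points. These sizes rest on an assumed R² and assumed correlations, and on a model that leaves arm means unconstrained at baseline. They are scenarios, not bounds. The point concerns efficiency and pre-specification, not validity. It merits a change because the remedy is nearly free; confidence in the size is medium.

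**What to change.** State in the primary-analysis paragraph that the mixed model will include site-by-visit and HbA1c-stratum-by-visit fixed effects, with levels as used at randomisation. State also that these terms enter regardless of observed baseline balance. Main effects alone would not achieve the purpose.

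As a side clarification, say which clinics form each stratification site. The text has four sites, and also says "The study will be conducted at 3 clinics in the Detroit area and 4 clinics in the Chicago area"; that is undefined rather than contradictory.

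The cost is two sentences and about four degrees of freedom per visit (three for four sites, one for the HbA1c level) out of about 194 participants. Sample size and conduct do not change.

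### Does the silence on how actual visit dates enter the primary mixed model put the 12-month comparison at risk?

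*Combined protocol and SAP*

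**What the plan says.** The document has no numbered sections, so places are given by paragraph topic.

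- **Intervention delivery.** Sessions two and three take place at diabetes clinic visits and "can be completed any time in the 12-month window after baseline assessment". Delivery is designed to take nine months if families attend quarterly.
- **Data collection schedule.** Collection runs on a different timetable from the sessions and "will occur at regularly scheduled visits conducted at six months and 12 months after baseline data collection". For the 12-month visit, "it must also occur at least 30 days from the date of the last intervention session", so that an HbA1c change due to the intervention has time to show. No latest date is given. The last visit is set at 18 months from baseline. The assurance on timing follows the 30-day rule: "The data analyses to be used in the study can accommodate varying lengths of time between data collection sessions".
- **Sample size.** The feasibility argument begins "Since outcome data will be collected during home visits".
- **Primary analysis.** A linear mixed model for repeated measures uses three differences, baseline minus each of the 6-, 12- and 18-month visits. "Three single degree of freedom contrasts will be defined by crossing the treatment arm factor with each time contrast", and the 12- and 18-month ones carry the primary hypotheses. They are labelled as end of treatment and six-month follow-up. Actual visit dates are not mentioned.

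**The concern.** The assurance names no mechanism. A mixed model can treat visits as categories or use actual time, and the two give different estimators of the 12-month contrast.

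Unequal timing is also built into the design, and it may differ by arm. A 3Ms family whose third session falls late in the window must wait for its 12-month visit, while no matching wait is described for controls. The two descriptions of where outcomes are collected add to the doubt, because a home visit can follow soon after day 30 whereas a clinic appointment might come later. Finally, a family that finishes at nine months is measured about 3 and 9 months after its last session, which fits the contrast labels poorly.

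At stake would be a primary contrast comparing arms at different times since baseline, and a modelling choice left open until the data are in hand.

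**Working it through.** **1. The plan's own figure.** Inputs from the sample-size paragraph: difference 0.6, SD of change 1.34, alpha 0.025, power 80%. Sidedness is not stated. A two-sided t-test needs 96.1 per arm, rounded up to 97 as stated; a one-sided test needs only 80. Attrition: 97 / 0.92 = 105.4, rounded up to 106. The stated numbers reproduce with a two-sided test, which is used below.

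- Standard error of the arm difference: 1.34 × √(2/97) = 0.192.
- Critical value for two-sided 0.025: 2.241.
- Power at 0.6 (normal approximation): Φ(0.6/0.192 − 2.241) = 81%.

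**2. How the model codes time.** Three single-degree-of-freedom contrasts, each a difference between baseline and one named visit and each crossed with arm, describe a four-level visit factor by arm. A model in continuous calendar time would not naturally produce them. The statement that unequal intervals can be accommodated is true of a mixed model and does not contradict this coding.

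**3. How long the forced delay can be.** The 30-day rule binds only if the last session falls after day 365 − 30 = 335. A session on day 365 moves the earliest permitted visit to day 395, or 13.0 months. The gap to the 18-month visit (about day 548) then falls from about 183 to about 153 days. Thirty days is the largest forced delay; last sessions spread evenly over days 335 to 365 would give a mean of 15 days.

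**4. Size of the bias with visits as a factor.** The documents give neither the underlying HbA1c trend nor the share of families delayed. Assume a rise of 0.2 to 0.8 points a year and 20% to 50% of 3Ms families delayed, with no such delay among controls.

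Bias = drift × share delayed × delay in years.

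| Drift per year | Share | Delay (days) | Bias (points) |
|---|---|---|---|
| 0.2 | 20% | 30 | 0.2 × 0.20 × 30/365.25 = 0.003 |
| 0.8 | 50% | 15 | 0.8 × 0.50 × 15/365.25 = 0.016 |
| 0.8 | 50% | 30 | 0.8 × 0.50 × 30/365.25 = 0.033 |

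**5. Direction and consequence.** With HbA1c rising, a later reading is higher, so 3Ms looks worse. At the top value:

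- Bias relative to the standard error: 0.033/0.192 = 0.17.
- Power: Φ((0.6 − 0.033)/0.192 − 2.241) = 76%.
- Chance of a false benefit with no true effect: Φ(−2.241 − 0.17) = 0.8%, below the nominal 1.25%.
- Chance of a false harm: Φ(−2.241 + 0.17) = 1.9%, against the same 1.25%.

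**The case for a change.** The strongest case for acting is analytic freedom. If the time variable is unstated, someone could add a visit-date term after seeing the data. In 3Ms, lateness partly reflects poor attendance, so such a term could absorb the worse control of poor attenders and move the estimate towards 3Ms. The mechanism is real, but it needs two things the documents do not supply: a visit-date covariate, which no paragraph proposes, and an extra HbA1c rise among poor attenders, whose size would have to be invented. The plan's covariate provision covers sociodemographic and clinical variables, considered when baseline values differ between arms. A follow-up visit date does not fit that description.

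The wording on setting is untidy, and no upper window is stated. If collection really waited for another clinic appointment, the delay would be longer and the bias would grow in proportion, with the same sign under a rising trend. But the plan separates data collection from the session timetable, describes the blood kit as suitable for home use, and names home visits outright. Home follow-up is therefore the more natural reading, and it keeps the forced delay near 30 days.

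On labels, 12 months is the outer limit for receiving sessions, so calling that visit the end of treatment is defensible. The contrasts are fixed by time from baseline whatever they are called.

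What stands is that the time variable is implied rather than stated, the visit has no latest date, and the two phrases about setting should read alike.

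**Conclusion.** No change to the plan is needed. The contrasts as written already imply visits as a factor, so a sentence saying so would record the existing analysis without altering it. Under that analysis the 30-day rule costs between 0.003 and 0.033 HbA1c points of a 0.6-point target. It works against 3Ms and takes power from 81% to 76% at the extreme.

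This rests on an assumed upward trend of 0.2 to 0.8 points a year, 20% to 50% of 3Ms families delayed by the full 30 days, and home collection. A falling trend would reverse the sign. The delay is also a fair price for the rule's purpose, since an HbA1c reading taken sooner after the last session could miss part of a genuine effect.

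A model in actual visit time offers no clear gain, because it brings its own assumptions about the shape of change between visits. Tabulating actual visit times by arm is ordinary reporting and would show whether the delays were as small as expected. The visit window and the wording on setting are clerical matters that leave the primary result unaltered.

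### Pre-specify a common baseline HbA1c mean for the 12- and 18-month primary contrasts: a free gain in precision, not a sizing error

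*Combined protocol and SAP*

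**What the plan says.** The document has no numbered sections, so places are named by content.

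- **Primary analysis.** HbA1c at baseline, 6, 12 and 18 months is analysed by a linear mixed effect model (LME). Time is split into baseline-minus-follow-up contrasts, and "Three single degree of freedom contrasts will be defined by crossing the treatment arm factor with each time contrast". The 12- and 18-month contrasts carry the primary hypotheses.
- **Sample size.** The planned analysis is "approximated by a t-test for the change in HbA1c from baseline to 12 or 18 months", with SD of change 1.34, difference 0.6, alpha 0.025, 80% power and 97 per arm net of loss (106 enrolled). The paragraph adds that "even patients with incomplete data will contribute to the effective net sample size".
- **Covariates.** "Potential control variables include sociodemographic and clinical variables". Then: "If the baseline values are not equal for the intervention and control groups, we will consider adding covariates before testing the intervention effect".
- **Moderators.** "Product terms involving the moderator and the time x treatment contrasts will be added to the LME model one at a time". This is the only mention of product terms beyond arm by time.
- **Randomization.** Allocation is by "block randomization within 8 strata defined by the four sites and HbA1c level", with the most recent HbA1c cut at 9.5%. The analysis text puts neither stratification factor in the model.

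Nowhere is baseline HbA1c named as a covariate, and nowhere are the arms given the same baseline mean.

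**The concern.** Baseline HbA1c is used, but only by subtraction. Crossing arm with time ordinarily brings in an arm main effect, so the two baseline means are estimated freely. With complete data the arm-by-time contrast is then the plain difference in mean change. That treats a one-point difference at baseline as worth exactly one point at follow-up. If the true slope is below 1, subtraction over-corrects and leaves avoidable noise in both primary tests. A model that estimates the slope, or that uses the fact that randomized arms share a baseline mean, removes this noise with data already collected.

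The covariate sentence cannot be relied on to do this. It depends on the observed data, gives no criterion for inequality, commits only to considering covariates, and does not name HbA1c. It also leaves a discretionary model choice immediately before the primary test.

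At stake are precision, and a clear statement of which of two codings, with different standard errors, is the primary analysis.

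**Working it through.** **1. The plan's own figure.** Inputs from the sample-size paragraph: SD of change 1.34, difference 0.6, alpha 0.025, n = 97 per arm.

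- SE = 1.34 × √(2/97) = 0.192; 0.6/0.192 = 3.12.
- Non-central t, 192 df, two-sided 0.025: power 80.4% at n = 97, and 79.96% at n = 96. So 97 reproduces.
- The plan does not state sidedness. One-sided 0.025 would need only 80 per arm, so 97 implies a two-sided test.
- 97/0.92 = 105.4, rounded up to 106 enrolled.

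**2. Adjusted versus change-score variance.** Let ρ be the baseline-to-follow-up correlation and k the ratio of follow-up SD to baseline SD. Neither is in the documents, so both are assumed. The slope of follow-up on baseline is ρk.

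Variance ratio = k²(1 − ρ²) / (1 + k² − 2ρk).

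- With k = 1 this is (1 + ρ)/2. The SE of 0.192 becomes 0.167, 0.177, 0.183 and 0.188 at ρ = 0.5, 0.7, 0.8 and 0.9. Coding the LME with no arm difference at baseline gives the same SEs (complete data).
- With k = 1.25 and ρ = 0.8 the slope is 1, and the ratio is 1.5625 × 0.36 / (1 + 1.5625 − 2.0) = 0.5625/0.5625 = 1. There is no gain.

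Put into the same t-test formula with k = 1, these SEs give 90.9%, 86.8%, 84.7% and 82.6%, against 80.4%. They ignore the stratification and so overstate most of the gains.

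**3. Allowing for stratified randomization.** Simulation: 194 families, 8 strata, blocks of 4, baseline normal and centred at the cut, k = 1, SD of change 1.34. Block size, the position of the cut, k and ρ are assumptions. There were 35,000 runs per cell (Monte Carlo error about 0.2 points for power and 0.08 for type I error).

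| ρ | Planned power | Adjusted power | Gain (points) | Planned type I error | Equivalent n per arm |
|---|---|---|---|---|---|
| 0.5 | 82.4% | 90.7% | 8.3 | 1.5% | 109 |
| 0.7 | 81.4% | 86.9% | 5.5 | 1.8% | 103 |
| 0.8 | 81.2% | 84.6% | 3.4 | 2.0% | 101 |
| 0.9 | 80.8% | 82.3% | 1.5 | 2.2% | 99 |

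The last column is the size, in place of 97, at which the planned contrast would match the adjusted one in actual sampling variance.

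A second simulation gave 82% vs 91%, 82% vs 86% and 81% vs 83% at ρ = 0.5, 0.7 and 0.9, with planned type I error of 1.5% to 2.3%. The gain at ρ = 0.7 is therefore best read as about 5 points.

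The type I error is low because the usual standard error ignores the stratification. At ρ = 0.5 the change-score estimate has an actual SD of 0.178 but a reported SE of 0.192. Adjusted type I error was 2.4-2.6%.

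**4. Sensitivity.**

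- The stratifier is the most recent HbA1c, not the study baseline value. If the two correlate 0.8 (assumed), planned versus adjusted power is 81.7% vs 91.0%, 81.1% vs 86.7%, 80.8% vs 84.8% and 80.6% vs 82.5% at the four values of ρ.
- With slope 1 and stratification (k = 1.25, ρ = 0.8), power is 80.9% vs 80.8%.

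**5. A covariate added only as a main effect.** With complete data, a covariate that is constant over visits drops out of within-family contrasts. In one simulated complete data set the 12- and 18-month contrasts were −0.6643 and −0.7665 (SE 0.1917), both with and without a clinic HbA1c main effect. With covariate-by-visit terms they became −0.5936 and −0.6995 (SE 0.1854). The plan does not say which form a covariate would take, so this shows only what could happen.

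**The case against.** **No error is shown.** The contrast is unbiased, the sample size matches it, and baseline HbA1c already enters by subtraction and through the strata. All of this stands. A reader might infer that the trial is mis-sized or the test invalid. The documents support neither: 97 reproduces, and the planned test errs on the conservative side.

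**The defect may not exist.** The text names a main effect of time and three arm-by-time contrasts, but never an arm main effect. If the LME is coded without one and with baseline as reference, the common baseline mean is already there and nothing is lost. This stands as a limit on the claim. The t-test on change in the sample-size paragraph favours the free-baseline reading but does not settle it, and a plan should say which model is primary.

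**The size rests on assumptions.** The documents give only the SD of change. A reader might take a gain of about 10 points (80.4% to 90.9%) as the headline. That figure ignores the stratification and assumes ρ = 0.5, so the stratified range is the fair one.

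**The covariate sentence might be enough.** A reader might infer the opposite: that it would almost never be triggered, or could never affect the primary tests. Neither follows. It refers to baseline values generally, not HbA1c alone, and sets no criterion, so no trigger rate can be derived from it. The main-effect result in the working holds for complete data, whereas the plan expects some incomplete records.

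**Conclusion.** The point holds as a free improvement in precision and pre-specification. On the usual reading of the crossed contrasts, the primary tests are unadjusted comparisons of change, and nothing in the plan can be relied on to adjust for baseline HbA1c.

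Adjustment is worth about 8, 5, 3.5 and 1.5 points of power at correlations of 0.5, 0.7, 0.8 and 0.9, from a planned 81-82%. This rests on equal visit SDs, blocks of 4 and a cut at the baseline mean. The gain is nil if the slope is 1 or if the common baseline mean is already coded. The conservatism of the planned test (type I error about 1.5% to 2.3% against 2.5%) is a side effect of the same omission. Apart from about one degree of freedom, adjustment has no statistical cost.

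**What to change.** Keep the LME and the 12- and 18-month contrasts. Pre-specify one primary model: baseline HbA1c stays as an outcome, with visit effects, arm-by-post-baseline-visit effects and no arm difference at baseline. Apply it whatever the observed balance, and let it replace the conditional covariate sentence as far as HbA1c is concerned. The plan names no covariance structure; state one in the same place, because the gain comes through the modelled correlation between baseline and follow-up.

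A model of the post-baseline values alone, with baseline as covariate, should not be offered as an alternative. It would leave the primary analysis open again, and it would drop families with no follow-up HbA1c although the plan commits to including all randomized participants. With the common baseline mean, every randomized family with a baseline HbA1c stays in the fit.

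Cost: one or two sentences. If the LME is already coded this way, the change only records it. No new families, visits or measurements are needed, and the sample size need not change.
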